Individuals with stroke admitted as inpatients to the Shirley Ryan AbilityLab will be asked to potentially enroll in the study. A thorough review of the participant's medical history will be completed by licensed physical therapists, and medical clearance will be obtained from the individual's medical team. The study coordinators will assess eligibility based on inclusion criteria, obtain informed consent, and answer any questions from the participant and/or his/her power of attorney (POA). If the participant is deemed unable to consent by the primary medical team, consent will be obtained from the individual's power of attorney (POA). Following informed consent, participants will undergo a physical evaluation and screening exam by a licensed physical therapist. Once they are enrolled, baseline outcome measures will be assessed by a physical therapist [See Clinical Assessments section].

If a participant is placed in the intervention group receiving gait training via the EksoNR exoskeleton, additional steps will be taken during baseline assessments to ensure the participant is appropriate for use of the EksoNR. These measures include upper and lower extremity range of motion, upper and lower extremity strength, spasticity, transfer status, skin integrity, and then three specific body measurements to assist with setting up the EksoNR exoskeleton. The three body measurements include hip width measured in sitting, upper leg lengths measured supine on a mat table, and lower leg lengths measured sitting on the edge of the mat table with feet supported on a step. Measurements are compared bilaterally and then converted to EksoNR values using a chart from Ekso Bionics (See User Manual). All assessments will be completed by a trained physical therapist to ensure standardization and safety of the participant.

Procedures during treatment:

After the baseline testing is completed, participants will complete between 9-24 training sessions dependent on their length of stay. These training sessions will occur in the inpatient Legs + Walking Lab with a licensed physical therapist and will last up to 90 minutes. Each session will be customized based on the participant's functional capacity with the goal of maximizing stepping practice.

Body-weight-supported treadmill + overground gait training group:

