Upon arrival to the session, a Polar OH1 Optical Heart Rate Sensor and an ActiGraph GT9X Link will be placed on the participant. Vitals including heart rate, blood pressure, oxygen saturation, and rating of perceived exertion (RPE) will be assessed at the beginning, during walking, and at the end of the session. The physical therapist will then assist with transferring the participant into the EksoNR exoskeleton while in sitting, adding wedges and/or padding as needed. Multiple straps will be applied bilaterally at the shoulders, across the abdomen, midthighs, below the knees, and around the shoes. Once the participant is safely secured into the EksoNR exoskeleton, they will be assisted into standing to begin gait training. The physical therapist will encourage them to maximize the number of steps during gait training for up to 60 minutes total with a targeted intensity of 70-85% of age-predicted heart rate maximum. The participant's response to exercise will be continuously monitored via vital monitoring and the participant's subjective report. Therapist will also utilize feedback from the EksoNR to guide the treatment session. The participant can request standing or seated rest breaks during the session as needed. If, at any time, the participant's heart rate exceeds 90% of age-predicted heart rate maximum, a seated rest break will be initiated by the therapist to allow the heart rate to return to baseline levels prior to returning to the walking protocol. The physical therapist may modify the EksoNR programming parameters to provide the appropriate challenge. Upon completion of each session, the EksoNR exoskeleton will be doffed in sitting, and the participant's skin will be thoroughly assessed. Some sessions may include additional overground gait training to assess the carry-over of learning. In this case, the physical therapist will provide the appropriate physical assistance, assistive device, and bracing based on current functional level.

Clinical assessments:

All assessments will be performed by a licensed physical therapist as per the standard of care at the Shirley Ryan AbilityLab. The participant will be given rest breaks as needed between tests to minimize fatigue. The physical therapist will provide the appropriate physical assistance, assistive device, and bracing based on current functional level.

Clinical assessments performed at enrollment and weekly

1. Scale for Contraversive Pushing (SCP)

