IRB Project #: STU00213155, Medical Clearance Form (v01) 08/05/2020Page 5 of 17Principal Investigator: [name], PT, PhDHRP-593 / v03152019

- 2. Burke Lateropulsion Scale (BLS)
- 3. 10 Meter Walk Test (10MWT)
- 4. 6 Minute Walk Test (6MWT)
- 5. Berg Balance Scale (BBS)
- 6. Function in Sitting Test (FIST)
- 7. Functional Independence Measure (FIM)
- 8. Quality Indicators (QI)
- 9. Manual Muscle Test (MMT)
- 10. Range of Motion (ROM)
- 11. Modified Ashworth Scale (MAS)

Clinical assessments performed each session

- 1. Step count
- 2. Time spent in 70-85% of age-predicted maximum target heart rate zone
- 3. Rating of perceived exertion (RPE)
- 4. Therapist heart rate
- 5. Therapist RPE
- 6. Therapist Numerical Rating Pain Scale

Description of clinical assessments:

- Scale for Contraversive Pushing (SCP): The SCP is a three-item test used to measure lateropulsion, scored on a three point ordinal scale. It rates a participant's action/reaction of maintaining or changing a position in both sitting and standing. A score >0 indicates the presence of CPB.
- 2. Burke Lateropulsion Scale (BLS): The BLS is a five-item test used to measure lateropulsion, scored on a four to five point ordinal scale. It rates a participant's action/reaction of keeping or changing a position in sitting, standing, rolling in supine, transfers, and walking.
- 3. 10 Meter Walk Test (10MWT): The 10MWT is a common clinical measure of gait speed. Participants will be directed to walk at their comfortable, self-selected speed. Participants will be positioned at the start line and instructed to walk the entire 10 meter distance while the therapist times the middle six meters. The distance before and after the timed course are meant to minimize the effect of acceleration and deceleration. Time will be recorded using a stopwatch and recorded to the one hundredth of a second (ex: 2.46 sec). The test will be performed two times at self-selected speed with adequate rest in between. The average of the two times should be recorded. The test will then be repeated with the participants directed to walk at their fast but safe speed. Appropriate assistive devices, bracing, and the minimal amount of physical assistance from the physical therapist will be applied.

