- 9. Manual Muscle Test (MMT): The MMT is a procedure for evaluating the strength of 16 individual muscles relative to gravity and manual resistance. Instructions are provided to the participant before testing each muscle. A muscle is isolated, and gradual external force is applied at a right angle to the muscle's long axis. Each muscle is scored on a graded scale of "weak" to "strong" based on the participant's ability to resist the external force. The test is first completed for muscles on the unimpaired side to determine normal strength before being repeated on the impaired side. Weaker participants may be tested while lying prone (gravity eliminated).
- 10. Passive Range of Motion (ROM): The purpose of this test is to evaluate a participant's passive range of motion in the joints of the hips, knees, and ankles.
- 11. Modified Ashworth Scale (MAS): The MAS is a 6-point ordinal scale used to grade the amount of hypertonicity in individuals with neurological diagnoses. A score of 0 on the scale indicates no increase in tone while a score of 4 indicates rigidity. Tone is scored by passively moving the individual's limb and assessing the amount of resistance to movement felt by the examiner.
- 12. Step count: The number of steps taken during each session will be measured using ActiGraph GT9X Link activity monitors. These devices are small accelerometers that can be worn on a belt and/or on the ankle to record steps and Kcals during an activity. The therapist leading the intervention session will apply the ActiGraph at the beginning of each intervention session and remove it upon completion.
- 13. Age-predicted maximum heart rate zone: The target range of 70-85% of age-predicted maximum heart rate will be calculated for each participant utilizing HRmax = 208 [0.7 × age] as developed by Tanka et al in 2001.¹⁴ It is recommended that clinicians should apply moderate to high-intensity walking training to improve walking speed and endurance individuals poststroke.^{1,15} We will record the amount of time participants spend in their precalculated target zone during each gait training session utilizing the Polar OH1 Optical Heart Rate Sensor.

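### EksoNR placement can be known before the therapist-scored baseline is complete, and no masking is described, so knowledge of the group can influence baseline scores

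*Protocol*

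**What the plan says.** In the Protocol, under Procedures Involved (screening, enrollment and baseline procedures), consent is followed by a screening examination. Then: "Once they are enrolled, baseline outcome measures will be assessed by a physical therapist". The next paragraph turns to one group: "If a participant is placed in the intervention group receiving gait training via the EksoNR exoskeleton, additional steps will be taken during baseline assessments". The stated purpose is "to ensure the participant is appropriate for use of the EksoNR". On content it says: "These measures include upper and lower extremity range of motion, upper and lower extremity strength, spasticity, transfer status, skin integrity". Three body measurements complete the list: hip width, upper leg lengths and lower leg lengths.

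The section on clinical assessments lists eleven measures under the line "Clinical assessments performed at enrollment and weekly". The list is not divided by group. It includes the two pushing scales (SCP, BLS), the 10MWT and 6MWT, the BBS, FIST and FIM, and also MMT, ROM and MAS. A licensed physical therapist performs all of them. The section on qualifications and resources has experienced physical therapists leading both assessment and treatment. No passage describes an assessor unaware of the group, or says that baseline is closed before the group is made known. The session table under Study Timelines allows one or two enrollment and baseline sessions of 60 to 120 minutes each.

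**The concern.** Baseline is the reference point for any statement about improvement, and the protocol intends to compare the two groups and draw conclusions on the efficacy of each. If the therapist scoring baseline already knows the group, expectation can enter the score. The background section states the hypothesis that the EksoNR will be efficacious, so the staff are not without expectations. An error of this kind sits in one arm's starting values. It carries into each comparison that uses baseline, and it cannot be corrected afterwards because the true score was never recorded. The order of placement, baseline testing and device checks is a protocol procedure, so an analysis plan could not repair it.

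**Working it through.** The protocol gives no figure to reproduce, so the check compares passages and then applies simple algebra.

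**1. Order.** Baseline outcomes follow enrollment. The EksoNR steps are taken during baseline, for people already placed. Training starts only after baseline testing. The text therefore fixes baseline before training, but it does not fix baseline before placement. It also leaves open whether the outcome tests come before or after the EksoNR steps.

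**2. Which measures are exposed.** SCP, BLS, BBS and FIST are ordinal scales rated by the therapist. MMT and MAS rest on the resistance the examiner judges. The 10MWT and 6MWT allow the least physical help needed, and the therapist decides how much that is.

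**3. What the EksoNR group has in addition.**

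| EksoNR step | Counterpart in the common enrollment battery |
|---|---|
| Lower-limb range of motion | Item 10, which is to "evaluate a participant's passive range of motion in the joints of the hips, knees, and ankles" |
| Upper-limb range of motion | None stated |
| Strength | Item 9 (MMT, 16 muscles, not named, so upper-limb coverage is unclear) |
| Spasticity | Item 11 (MAS) |
| Transfer status | Scored within the FIM, item 7 |
| Skin integrity | None at baseline |
| Hip width, upper and lower leg lengths | None |

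Most of the content is common to both groups. What is clearly extra is upper-limb range of motion, a skin check and three body measurements. The concern therefore rests on knowledge of the group, not on a heavier test load.

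**4. Size.** Let X be the baseline mean and Y the follow-up mean, in groups E (EksoNR) and T (treadmill).

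- Difference in change: (Y_E - X_E) - (Y_T - X_T). Replacing X_E by X_E + d moves it by -d, which is d in size.
- Baseline-adjusted difference: (Y_E - Y_T) - b(X_E - X_T). The same replacement moves it by -b x d. This treats d as a common shift within the arm, so that b is unchanged.
- If follow-up scores in E are also shifted, by e, the two results become e - d and e - b x d. Masking the later visits sets e = 0 and leaves -d or -b x d.

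Sample size appears in none of these expressions. The document supplies neither d nor b. If b is assumed to lie between 0 and 1, the adjusted error lies between 0 and d in size.

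**The case against.** The strongest reply is that the order is ambiguous rather than wrong. The protocol mentions baseline outcomes first and the EksoNR steps in the next paragraph, so outcomes could be taken first, with placement and device checks afterwards. Staff are trained to give the outcome tests in a standardized way, which limits scorer variation. On this view, what is left is the baseline instance of a general absence of masking.

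Part of this stands. The text does not prove that any outcome is scored after placement. But it does not prevent it either, and standardized training does not hide the group. The baseline part also has its own remedy, because reordering protects baseline even where later masking is impractical.

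A reader might infer more than the document supports:

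- *That the tests are mostly EksoNR-only.* They are not: MMT, ROM and MAS are taken at enrollment in both groups, and transfers are scored within the FIM.
- *That the extra steps share a sitting with the outcome tests.* Baseline may take one or two sessions, and the order of tests is not given.
- *That fatigue worsens the EksoNR baseline.* Rest breaks are provided for everyone, and the body measurements are taken sitting or lying down.
- *That the bias favours EksoNR.* Either direction is possible.
- *That people found unsuitable are dropped from or moved out of the EksoNR group.* The section does not say what happens to them.

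**Conclusion.** The point holds as an open route to bias, not as demonstrated bias. Placement can be known before the therapist-scored baseline is complete, and the protocol describes nothing that shields those scores. The error in the difference in change equals the baseline shift d in size, or b x d after adjustment; d is unknown in sign and amount and may be zero. This assumes that the analysis uses baseline; a comparison of follow-up scores alone would not carry this error. The same sentence raises a linked matter: the extra steps also check suitability for the device, after placement and in one arm. That check should not be left where it can act on one group only. The point deserves a change because the remedy is cheap and cannot be applied once baselines have been scored.

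**What to change.** Reword the section on screening, enrollment and baseline procedures to give this order:

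1. After consent, settle suitability for the EksoNR for every participant before placement. Use the range of motion, strength and spasticity data already collected from everyone. This changes when the existing device criteria are applied, not what they are.
2. Complete all common baseline outcomes in the same way for every participant, and lock the record.
3. Only then assign or disclose the group.
4. Take the EksoNR sizing measurements as a separate step that contributes no outcome data.

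If this order cannot be guaranteed in practice, name a baseline assessor who does not know the group.

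The cost of the core change is a reordering of existing steps, with no new outcome tests and no added staff. Where a device criterion depends on hip width or leg length, settling it before placement means taking that measurement in everyone, a short addition to the screening examination. The fallback assessor would need some staff time.

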The commercially available Woodway + LokoStation [Refer to Figure 2.A] is intended to assist an individual when performing locomotor therapy under the supervision of a trained physical therapist. The purpose of the body weight support system is to facilitate ambulation for participants with walking difficulties due to cerebral, spinal, neurogenic, muscular, or osseous causes. See attached user manual.

EksoNR Exoskeleton

The commercially available EksoNR [Refer to Figure 2.B] is intended to assist an individual when performing ambulatory functions under the supervision of a physical therapist who has completed formalized training. It is approved by the FDA for use in individuals with stroke diagnoses. The EksoNR is an under-actuated lower extremity exoskeleton with actuation at the knee and hip joints and a passive ankle. The device enables individuals with any amount of lower extremity strength to stand up and walk overground with a natural, weight bearing, reciprocal gait pattern. The EksoNR utilizes cooperative gait rehabilitation algorithms to vary the amount of assistance provided to each user for an individualized therapy experience. This method allows the exoskeleton to work with a user's existing strength and provide only the extra effort required to complete a maneuver correctly and safely. Walking is achieved by shifts in the wearer's weight, which activate sensors in the footplate and initiate steps. See attached user manual.

[figure not shown]

Figure 2. Gait intervention systems. A) Woodway Treadmill System. B) EksoNR Exoskeleton.

STUDY ENDPOINTS

Study endpoints:

The study ends when the participant completes the intervention protocol and outcomes assessment and when data has been collected and analyzed. The study may also end if the participant discharges from the inpatient setting prior to completing the intervention protocol. The participant may choose to withdraw from the study at any time.

Safety endpoints:

Participant enrollment in this study will be terminated if the research or medical team determine that the participant is no longer medically stable to continue participation. Any adverse events will be documented thoroughly.

PROCEDURES INVOLVED

Screening, enrollment, and baseline procedures:

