Upon arrival to the session, a Polar OH1 Optical Heart Rate Sensor and an ActiGraph GT9X Link will be placed on the participant. Vitals including heart rate, blood pressure, oxygen saturation, and rating of perceived exertion (RPE) will be assessed at the beginning, during walking, and at the end of the session. The physical therapist will then assist with donning a walking harness with padding (as needed) in sitting or standing based on the participant's current functional capacity. The participant will be assisted onto the Woodway treadmill via ramp

IRB Project #: STU00213155, Medical Clearance Form (v01) 08/05/2020Page 4 of 17Principal Investigator: [name], PT, PhDHRP-593 / v03152019

while seated in a wheelchair. The participant will be clipped into the body weight support system, assisted into standing, and provided the appropriate amount of body weight support to allow for successful stepping practice. During walking, the physical therapist and a rehabilitation technician will provide physical assistance as necessary to advance the participant's limbs. The participant will be instructed to maximize the number of steps during gait training for up to 60 minutes total with a targeted intensity of 70-85% of age-predicted heart rate maximum. The participant's response to exercise will be continuously monitored via vital monitoring and the participant's subjective report. The participant can request standing or seated rest breaks during session as needed. If, at any time, the participant's heart rate exceeds 90% of age-predicted heart rate maximum, a seated rest break will be initiated by the therapist to allow the heart rate to return to baseline levels prior to returning to the walking protocol. The physical therapist may modify training parameters including: treadmill speed, incline, direction (forward, backward), and amount of body weight support in order to provide the appropriate amount of challenge. Upon completion of each session, the harness will be doffed in standing or sitting, and the participant's skin will be thoroughly assessed. Some sessions may include additional overground gait training to assess carry-over of learning. In this case, the physical therapist will provide the appropriate physical assistance, assistive device, and bracing based on current functional level.

EksoNR gait training + overground gait training group:

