- 14. Borg Rating of Perceived Exertion (RPE): The Borg RPE is a tool to measure the subjective report of effort, exertion, and fatigue during physical work. It consists of a 15-point scale from 6-20, in which 6=no exertion and 20=absolute maximum exertion. It is presented to the participant in written format with descriptors to standardize the report of perceived exertion across tasks.
- **15.** Numerical Rating Pain Scale (NPRS): The NPRS is used to measure the subjective report of pain intensity. It consists of an 11-point scale, 0-10, in which zero indicates no pain and ten indicates the most intense pain imaginable. In this study, therapists will be provided a written format of the NPRS to report their perceived pain following delivery of each intervention session.

IRB Project #: STU00213155, Medical Clearance Form (v01) 08/05/2020Page 7 of 17Principal Investigator: [name], PT, PhDHRP-593 / v03152019

DATA COLLECTION AND ANALYSIS

Data from participants will be collected during their hospital stay, including clinical and functional outcomes. The complete medical history of the participants, including physical findings, radiological reports such lesion size, location, type, medications, intervention training parameters and therapist-assessed clinical outcomes may also be collected (See Clinical Assessments section). Participants' records and data will be kept confidential and in compliance with HIPAA requirements. Research data will be de-identified and stored in locked cabinets in the lab with access only to research staff. Electronic data will be de-identified and kept on secure, password protected files, and password protected computers. Analysis will be completed to compare the two intervention groups and draw conclusions on the efficacies of both interventions.

Photographs, audio, and video recordings:

We may photograph, audio, or video record the participants during the study to be used for scientific publications and scholarly presentations only. The photographs will be de-identified, meaning that the face of the participants will not be shown. Participants will be given the choice to accept or decline this optional aspect during the informed consent process. Their choice will not impact their participation in the study.

STUDY TIMELINES

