Study documentation will be collected and stored and kept confidential and compliant with HIPAA requirements.

All personal information (names, addresses, email or phone numbers, etc.) gathered for this study that can identify participants will be kept secure to protect their privacy and will never be shared with any person or entity at any time. Data collected during the study and shared with others will reference participants only by an alphanumeric code. The "master list" linking personal information to the alphanumeric code will not be shared and will be kept in a secure location.

QUALIFICATIONS TO CONDUCT RESEARCH AND RESOURCES AVAILABLE Describe other resources available to conduct the research:

The Shirley Ryan AbilityLab services the stroke poption at a rate of approximately 300 new patients per year. The Shirley Ryan AbilityLab is a research hospital that maintains a research registry (greater than 750 participants). We will recruit inpatients to meet our enrollment goal and perform all research on site at the flagship hospital. The study team members are all employees of the Shirley Ryan AbilityLab. They are familiar with the study site and are experienced with the study population. There will be medical resources including a resident on call and nursing staff available 24 hours a day if needed in case of an emergency.

All study team members will be trained on the study protocol and procedures and have already been trained on how to safely administer all functional outcomes using standardized methods. The research staff consists of clinical researchers and licensed physical therapists trained in the safe use of therapeutic equipment, including the harness system used for locomotor training in the overground gait track and over all treadmills, gait belt use for assessments, and emergency management of the EksoNR exoskeleton. In addition, three therapists within the Legs + Walking team have completed both Part 1 and Part 2 of the EksoNR standardized training program. Experienced physical therapists will lead the assessment and treatment sessions. Finally, all research and therapy staff members have been CITI-certified and have Basic Life Support (BLS) training.

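### Therapist pain is rated only after each session, so this burden measure includes pain the therapist already had; a rating before the session is a cheap, minor improvement

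*Protocol*

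**What the plan says.** The protocol's Objectives section includes measuring therapist burden. The Background section gives reduced physical load on clinicians as part of the reason to expect benefit from the EksoNR. The list of assessments performed each session has three therapist measures: heart rate, RPE and the "Therapist Numerical Rating Pain Scale". The pain scale appears there once, with no before-and-after pair.

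In the description of clinical assessments, item 15 defines an 11-point intensity scale from 0 to 10 and sets its timing: "therapists will be provided a written format of the NPRS to report their perceived pain following delivery of each intervention session". No other timing for therapist pain is given. By contrast, both intervention descriptions take participant vitals and RPE at the start of the session, during walking and at the end.

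On who is treated by whom, the protocol says:
- Participants: "If a participant is placed in the intervention group receiving gait training via the EksoNR exoskeleton", with no randomisation described.
- Sessions in general: "These training sessions will occur in the inpatient Legs + Walking Lab with a licensed physical therapist".
- The EksoNR is for use "under the supervision of a physical therapist who has completed formalized training", and the resources section states that "three therapists within the Legs + Walking team have completed both Part 1 and Part 2 of the EksoNR standardized training program".
- No rule assigns therapists to groups.

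**The concern.** Item 15 asks for pain intensity after the session and does not restrict it to pain caused by the session. A therapist who arrives with a sore back reports that soreness along with anything the session added. If the groups are compared on this score, existing pain enters the comparison.

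The effect can take two forms. If pre-session pain is similar in the two groups, it is noise. If it differs, part of that difference appears as a difference between interventions. The timing is a data-collection choice made in the protocol, so a later analysis plan can choose a model but cannot supply a rating that was never taken.

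**Working it through.** The protocol gives no standard deviation, correlation or effect size for therapist pain, so there is no planned figure to reproduce. From the protocol: 9 to 24 training sessions per participant (m). Assumed: pre-post correlation r = 0.3 to 0.8, and intraclass correlation p of the ratings within participant, central value 0.3, range 0.1 to 0.6.

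**Noise, single rating.** Adjusting for the pre rating leaves a fraction 1 - r² of the variance:
- r = 0.3: 0.91
- r = 0.5: 0.75
- r = 0.8: 0.36

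**Noise, participant mean over m sessions.** If the pre rating explains only session-to-session variation, the ratio of adjusted to unadjusted standard error is

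sqrt{ [p + (1 - p)(1 - r²)/m] / [p + (1 - p)/m] }.

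The formula ignores clustering by therapist.

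- p = 0.3, m = 9, r = 0.8: sqrt[(0.3 + 0.7 × 0.36/9) / (0.3 + 0.7/9)] = sqrt(0.3280/0.3778) = 0.932, a reduction of 6.8%.
- p = 0.3, m = 24, r = 0.3: sqrt[(0.3 + 0.7 × 0.91/24) / (0.3 + 0.7/24)] = sqrt(0.3265/0.3292) = 0.996, a reduction of 0.4%.

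Reduction in standard error:

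| p | m | r = 0.3 | r = 0.5 | r = 0.8 |
|---|---|---|---|---|
| 0.3 | 9 | 0.9% | 2.6% | 6.8% |
| 0.3 | 24 | 0.4% | 1.1% | 2.9% |
| 0.1 | 9 | 2.3% | 6.5% | 17.5% |
| 0.6 | 24 | 0.1% | 0.3% | 0.9% |

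A simulation with 15 participants per group and r = 0.8 agreed: 6.6% for p = 0.3, m = 9, and 17.9% for p = 0.1, m = 9. If the pre rating correlated equally strongly at participant and session level, the reduction would be 1 - sqrt(1 - r²), that is 4.6%, 13.4% and 40.0%. That is the upper limit. Many zero ratings would lower all these figures.

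**Bias.** A group difference d in mean pre-session pain carries slope × d into a post-only comparison. For slopes of 0.3 to 0.8:
- d = 0: no bias.
- d = 0.5 points: 0.15 to 0.40 points.
- d = 1 point: 0.3 to 0.8 points on the 0-10 scale.

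In a simulation with d = 1, no true effect and one value per participant, the post-only estimate was 0.51 (slope 0.5) and 0.79 (slope 0.8). The adjusted estimate was 0.00 in both. The values of d are illustrations; nothing in the protocol indicates what d is or its direction.

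**Adjustment or change score.** With equal standard deviations, a simple change score has variance 2(1 - r) times that of the post rating. At r = 0.3 that is 1.4, worse than the post rating alone; adjustment gives 0.91. A change score gains only when r exceeds 0.5.

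**The case against.** The strongest reply is that a rating after the session is a legitimate measure of therapist load as delivered, and that a paired rating refines it without correcting an error. That largely stands, and it is why the point is minor. Three further arguments have weight.

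- **The comparison is partly inferred.** The protocol states no group comparison for therapist pain specifically. Its general sentence on comparing the groups concerns efficacy. The Background rationale makes a burden comparison plausible but does not specify it, and therapist heart rate and RPE also measure burden.
- **Therapist effects.** If a therapist treats both groups and is identified in the data, a model with therapist effects can absorb that therapist's stable level of pain. It cannot absorb day-to-day pre-session pain.
- **Carry-over.** Sessions are planned three times weekly. If pain persists from one study session to the next, adjusting for the pre rating may remove some cumulative burden, which is part of what the objective concerns.

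A reader might infer that the comparison is biased because a few EksoNR-trained therapists form a separate pool. The protocol does not support this. It does not say that only the three named therapists deliver EksoNR sessions, or that they deliver no treadmill sessions. They belong to the Legs + Walking team, and all training sessions take place in that lab, which is compatible with shared staffing.

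**Conclusion.** The point holds as a minor improvement. The only timing stated for therapist pain is after the session, so the measure includes pain already present. Its main consequence is noise, and with repeated sessions the likely gain from removing it is small: about 0.4% to 6.8% of the standard error at an assumed intraclass correlation of 0.3. Across assumed values of 0.6 to 0.1 the range is 0.1% to 17.5%.

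The single-rating figures, where up to 64% of the variance could be removed (1 - 0.36), might tempt a reader to claim a large loss of precision. They do not carry over to a comparison of participants with 9 to 24 sessions each unless the correlation is equally strong at participant level, which is unknown.

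Bias is conditional on a difference between groups in pre-session pain. The protocol neither shows one nor guards against one, since it describes no randomisation and no rule assigning therapists to groups. The pushing-behavior outcomes are unaffected.

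**What to change.** In item 15 and in the per-session list, have the treating therapist give the 0-10 rating immediately before and immediately after each session, and record it with a therapist study code. Analyse the post rating adjusted for the pre rating, not as a simple change score, allowing for repeated sessions within participant and within therapist. Also report the unadjusted post-session rating, so that burden carried over from earlier study sessions stays visible. Without randomisation, adjustment may reduce a bias from differing therapists and not remove it fully.

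The cost is one extra rating per session. For the 10 completers named in the Background, that is 10 × 9 = 90 to 10 × 24 = 240 ratings. For the 30 participants in the study summary and accrual table, it is 30 × 9 = 270 to 30 × 24 = 720. No extra staff or visits are needed.
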